9 ASSESSMENT OF SAFETY

The safety variables will be evaluated during the Up-Titration Period (directly enrolled subjects only) and the Evaluation Period. For subjects who continue in the study until it ends, the Evaluation Period will include the EV through the FV. For subjects who prematurely discontinue the study, the Evaluation Period will include the EV through the EDV, followed by a 4-week Down-Titration Period (maximum), and a 2-week Safety (Drug-Free) Period.

9.1 Adverse events

9.1.1 Definitions

9.1.1.1 Adverse event

An AE is any untoward medical occurrence in a patient or clinical investigation subject administered a pharmaceutical product, which does not necessarily have a causal relationship with this treatment. An AE can therefore be any unfavorable and unintended sign (including an abnormal laboratory finding), symptom, or disease temporally associated with the use of a medicinal (investigational) product, whether or not related to the medicinal (investigational) product.

In order to ensure complete safety data collection, all AEs occurring during the study (ie, after signing the Informed Consent form), including any pretreatment and posttreatment periods required by the protocol, must be reported in the eCRF even if no investigational product was taken but specific study procedures were conducted. This includes all AEs not present prior to the initial visit and all AEs, which recurred or worsened after the initial visit.

Signs or symptoms of the condition/disease for which the investigational product is being studied should be recorded as AEs only if their nature changes considerably or their frequency or intensity increases in a clinically significant manner as compared to the clinical profile known to the Investigator from the subject's history or the Baseline Period.

9.1.1.2 Serious adverse event

Once it is determined that a subject experienced an AE, the seriousness of the AE must be determined. An SAE must meet 1 or more of the following criteria:

- Death
- Life-threatening
(Life-threatening does not include a reaction that might have caused death had it occurred in a more severe form.)
- Significant or persistent disability/incapacity
- Congenital anomaly/birth defect (including that occurring in a fetus)
- Important medical event that, based upon appropriate medical judgment, may jeopardize the patient or subject and may require medical or surgical intervention to prevent one of the other outcomes listed in the definition of serious

(Important medical events may include allergic bronchospasm requiring intensive treatment in an emergency room or at home, blood dyscrasias that do not result in inpatient hospitalization, or the development of drug dependency or drug abuse.)

- Initial inpatient hospitalization or prolongation of hospitalization

(A patient admitted to a hospital, even if released on the same day, meets the criteria for the initial inpatient hospitalization. An emergency room visit that results in admission to the hospital would also qualify for the initial inpatient hospitalization criteria. However, emergency room visits that do not result in admission to the hospital would not qualify for this criteria and, instead, should be evaluated for 1 of the other criteria in the definition of serious [eg, life-threatening adverse experience, important medical event].

Hospitalizations for reasons not associated with the occurrence of an AE [eg, preplanned surgery or elective surgery for a pre-existing condition that has not worsened or manifested in an unusual or uncharacteristic manner] do not qualify for reporting. For example, if a subject has a condition recorded on his/her medical history and later has a preplanned surgery for this condition, it is not appropriate to record the surgery or hospitalization as an SAE since there is no AE upon which to assess the serious criterion. Please note that, if the pre-existing condition has worsened or manifested in an unusual or uncharacteristic manner, this would then qualify as an AE and, if necessary, the seriousness of the event would need to be determined.)

9.1.1.2.1 Anticipated serious adverse events

The following Anticipated SAEs are anticipated to occur in the population studied in this protocol at some frequency that is independent of drug exposure.

This list does not change the Investigator's obligation to report all SAEs (including Anticipated SAEs) as detailed in [Section 9.1.2.3](#).

Table 9–1: Anticipated serious adverse events for the pediatric epilepsy population

MedDRA SOC	MedDRA PT
Congenital, familial and genetic disorders	Teratogenicity
General disorders and administration site conditions	Sudden unexpected death in epilepsy
Nervous system disorders	Convulsion ^a
	Status epilepticus
Pregnancy, puerperium and perinatal disorders	Abortion spontaneous
Psychiatric disorders	Psychotic behavior
	Abnormal behavior
	Anxiety
	Sleep disorder

MedDRA=Medical Dictionary for Regulatory Activities; PT=preferred term; SOC=system organ class

^a Convulsion if consistent with the seizure type known for the subject.

9.1.1.3 Adverse events of special interest

An AE of special interest is any AE that a regulatory authority has mandated be reported on an expedited basis, regardless of the seriousness, expectedness, or relatedness of the AE to the administration of a UCB product/compound. For this study, the AEs of special interest include:

- Autoimmune nephritis
- Nephritis
- Nephritis allergic
- Tubulointerstitial nephritis
- Tubulointerstitial nephritis and uveitis syndrome
- Potential Hy's Law, defined as $\geq 3 \times \text{ULN}$ ALT or AST with coexisting $\geq 2 \times \text{ULN}$ total bilirubin in the absence of $\geq 2 \times \text{ULN}$ ALP, with no alternative explanation for the biochemical abnormality, must ALWAYS be reported to UCB as an AE of special interest (ie, without waiting for any additional etiologic investigations to have been concluded). Follow-up information should then be reported if an alternative etiology is identified during investigation and monitoring of the subject.

9.1.2 Procedures for reporting and recording adverse events

The subject will be given the opportunity to report AEs spontaneously. A general prompt will also be given at each study visit to detect AEs, for example:

“Did you notice anything unusual about your health (since your last visit)?”

In addition, the Investigator should review any self-assessment procedures (eg, diary cards) employed in the study.

For LTFU subjects, AEs ongoing at the time the subject completed the core study should not be recorded in the eCRF at the EV, or any subsequent visit. Worsening of the AE should be recorded as a new AE. For all subjects, new AEs should be recorded in the eCRF at only the first visit at which they are reported and subsequently only if there is a change.

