Core study:	N01349	EP0065	Other ^a	Not applicable

form; EDV=Early Discontinuation Visit; EEG=electroencephalogram; EV=Entry Visit; GGT=gamma-glutamyltransferase; IVRS=interactive voice response system; LTFU=long-term follow-up; PedsQL=Pediatric Quality of Life Inventory; SAE=serious adverse event

^aOther" core studies include those other than EP0065 and N01349.

^bTo be obtained from the final visit of the core study and not recorded in the N01266 eCRF.

^cTo be obtained from baseline of the core study and not recorded in the N01266 eCRF.

^dVital sign measurements include blood pressure, pulse rate, and body temperature.

^eAny ongoing concomitant medication at the time the subject completed the core study should not be recorded in the N01266 eCRF. Changes in ongoing concomitant medications should be recorded in the N01266 eCRF.

^fAny ongoing AEs at the time the subject completed the core study should not be recorded in the N01266 eCRF. Worsening of the AE should be recorded in the N01266 eCRF as a new AE. A pharmacokinetic sample for determination of BRV plasma concentration should be taken whenever a subject experiences an SAE.

^gDrug return includes study medication intake recording and accountability.

^hFull laboratory assessments for safety include hematology and biochemistry (including hepatic monitoring of ALT, AST, ALP, total bilirubin, and GGT) for all subjects, endocrinology for LTFU subjects, and urinalysis for all subjects for whom sample collection is feasible as described in Section 9.2.1. Female subjects of childbearing potential will have a urine pregnancy test done at the site.

ⁱThe C-SSRS will be administered to subjects \geq 6 years of age. The "Since Last Visit" version of the C-SSRS will be used. If a subject turns 6 years of age during the study, the "Already Enrolled" version of the C SSRS should be completed at the first visit after the sixth birthday.

^jThe Bayley-III is applicable to subjects enrolled in English-speaking countries and in countries where a validated translation is available only and as follows:

- Core study N01349: all subjects
- Core study EP0065: subjects <18 months of age at baseline (Screening)
- Other core studies: subjects <18 months of age at baseline for the core study (as indicated in footnote c)

^kThe version of the Achenbach CBCL (CBCL/1½-5 or CBCL/6-18) should be in accordance with the subject's age.

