- For subjects \geq 2 years of age at V5 who have typical absence seizures, an EEG of at least 1 hour that includes hyperventilation and intermittent photic stimulation must be performed at V5 and yearly thereafter. For subjects prematurely discontinuing from the study, an at least 1-hour EEG may be performed at the EDV at the Investigator's discretion.
- For subjects <2 years of age at V5, an EEG of at least 24 hours must be performed for efficacy assessment at V5 and yearly thereafter until subjects reach 2 years of age. For subjects prematurely discontinuing from the study, an at least 24-hour EEG may be performed at the EDV at the Investigator's discretion.

^g No DRC or study drug will typically be dispensed at the FV. However, for subjects who complete the study but do not continue BRV treatment, study drug for down-titration will be dispensed.

^h The assessment of seizure types will be done at 6-monthly intervals (at the FEV and the YEV) for subjects <2 years of age.

ⁱ For subjects enrolled in N01266 who volunteered to participate in EP0065 and then returned to N01266, changes to ongoing concomitant medications during EP0065 will be recorded in the N01266 eCRF.

^j For subjects enrolled in N01266 who volunteered to participate in EP0065 and then returned to N01266, ongoing AEs that stop during EP0065 will be recorded in the N01266 eCRF.

^k Drug return includes study medication intake recording and accountability.

^l Full laboratory assessments for safety include hematology, biochemistry (including hepatic monitoring of ALT, AST, ALP, total bilirubin, and GGT), and

Table 5–2: Schedule of all study assessments for the Evaluation, Down-Titration, and Safety (Drug-Free) Periods (all subjects)

Period	Evaluation						Down-Titration	Safety (Drug-Free)
	Minimal Evaluation Visit (MEV)	Full Evaluation Visit (FEV)	Yearly Evaluation Visit/Final Visit (YEV/FV ^a)	Unscheduled Visit (UV)	Early Discontinuation Visit (EDV)	Down-Titration Visit (DTV) ^b		
Assessment								

endocrinology for all subjects and urinalysis for subjects for whom sample collection is feasible as described in Section 9.2.1. Female subjects of childbearing potential should have a urine pregnancy test done at the site at all laboratory assessment visits. Endocrinology testing will be performed at the YEV/FV.

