9.1.2.2 Rule for repetition of an adverse event

An increase in the intensity of an AE should lead to the repetition of the AE being reported with:

- the outcome date of the first AE that is not related to the natural course of the disease being the same as the start date of the repeated AE, and the outcome of “worsening”,
- the AE verbatim term being the same for the first and repeated AE, so that the repeated AE can be easily identified as the worsening of the first one.

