9.1.3 Follow-up on adverse events

An AE should be followed until it has resolved, has a stable sequelae, the Investigator determines that it is no longer clinically significant, or the subject is lost to follow-up.

If an AE is still ongoing at the end of the study for a subject, follow-up should be provided until resolution/stable level of sequelae, the Investigator no longer deems that it is clinically significant, or until the subject is lost to follow-up. If no follow-up is provided, the Investigator must provide a justification. The follow-up will usually be continued for 30 days after the subject has discontinued their IMP.

Information on SAEs obtained after clinical database lock will be captured through the Patient Safety (PS) database without limitation of time.

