12.3 Planned safety analyses

The long-term safety of BRV at individualized doses will be evaluated by means of the safety analyses. Summary tables will be presented over the Evaluation Period by 3-month periods and by categories of total duration of exposure.

All safety variables will be analyzed by descriptive methods on the Safety Set.

Treatment-emergent adverse events will be summarized by categories of total duration of exposure, 3-month period, Medical Dictionary for Regulatory Activities (MedDRA[®]) Primary

System Organ Class and Preferred Term in incidence tables. Separate tables will be provided by categories of total duration of exposure for AEs leading to withdrawal from the study and SAEs.

Laboratory values, vital signs, and weight will be summarized by 3-month period and visit. Possibly clinically significant treatment-emergent abnormalities for laboratory values, vital signs, and weight will be listed and summarized by 3-month period and visit. ECG abnormalities, as well as physical and neurological abnormalities, will also be listed by 3-month periods and visit.

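### Unworsened AEs carried over from a core study have no N01266 AE record when they lead to withdrawal, so the planned table of AEs leading to withdrawal can undercount for LTFU subjects

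*Protocol*

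**What the plan says.** Section 9.1.2 sets the recording rule for rollover subjects (LTFU): "AEs ongoing at the time the subject completed the core study should not be recorded in the eCRF at the EV, or any subsequent visit". One exception follows: "Worsening of the AE should be recorded as a new AE". Table 5-1 footnote f repeats the bar and the exception for the Entry Visit ("Worsening of the AE should be recorded in the N01266 eCRF as a new AE"), and Sections 8.3.1.1, 8.3.1.2 and 8.3.1.3 repeat both for each type of core study. Table 5-1 footnote b, attached to AE recording in all three LTFU columns, says that this information is taken from the last visit of the core study.

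Section 12.3 commits to separate tables, by duration of exposure, for "AEs leading to withdrawal from the study and SAEs". The primary objective (Section 3.1) is long-term safety and tolerability. The primary variables (Section 4.1) are treatment-emergent AEs and treatment-emergent SAEs.

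Section 6.3 has the main reason for ending participation entered in the eCRF, with a narrative in the source documents.

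**The concern.** LTFU subjects continue brivaracetam at the dose on which they finished the core study, so an AE that began on drug there may persist on drug in N01266. A lasting AE that does not worsen, but eventually makes a family stop, is a plain example of a long-term tolerability problem. The table of AEs leading to withdrawal is where a reader would look for it. That table needs an AE record that shows withdrawal as the action taken, and for this kind of event the Protocol forbids the record.

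This is not detail left for the SAP or the eCRF Completion Guidelines. Neither can tabulate, or permit, an entry that the Protocol rules out at every visit.

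**Working it through.** The Protocol states no figure for this point, so the check traces an event through the rules and then sizes the group that the rules cover.

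**Tracing one event.** Take an LTFU child with irritability that began in the core study, is still present at the Entry Visit, stays at the same intensity, and is the reason the family withdraws from N01266.

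1. Entry Visit: not recorded in N01266 (Section 9.1.2; Table 5-1 footnotes b and f). The core-study data hold the onset.
2. Later visits: still not recorded, because the bar extends past the Entry Visit and the event has not worsened.
3. General scope of AE collection (Section 9.1.1.1): "This includes all AEs not present prior to the initial visit and all AEs, which recurred or worsened after the initial visit". The event was present before the initial visit and has neither recurred nor worsened, so this section does not bring it in.
4. Withdrawal: the main reason is entered in the eCRF (Section 6.3). That counts the withdrawal, but it is not an AE record.
5. Table of AEs leading to withdrawal (Section 12.3): the event has no N01266 AE record, so it does not appear.

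**The same event in a directly enrolled child.** If the irritability began after consent, it is recorded when first reported and updated on change (Sections 9.1.1.1 and 9.1.2). The withdrawal attaches to that record and the event appears in the table. The gap is therefore confined to LTFU subjects.

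**Size of the group covered.** Inputs from Section 12.9: about 600 subjects planned, at least 100 of them directly enrolled.

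- LTFU subjects: at most 600 − 100 = 500
- Share: 500 / 600 = 83%

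**Number of withdrawals missed.** This equals (LTFU subjects) × p × q, where p is the share with an AE ongoing at core-study completion and q is the share of those who withdraw because of it without worsening. The Protocol gives neither. For scale only, assume p = 10% to 40% and q = 5% to 10%:

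- low: 500 × 0.10 × 0.05 = 2.5
- high: 500 × 0.40 × 0.10 = 20

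Both rates are assumptions with no basis in the document, so this range is not an estimate.

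**The case against.** The strongest reply is that the rule is deliberate and mostly right. An unworsened AE with onset in the core study is not a new event in N01266, and leaving it out avoids counting it twice. The onset is held in the core-study data, and LTFU subjects keep their subject number (Section 7.10), so records can be linked. SAEs are reported whatever their cause (Section 9.1.2.3). The withdrawal itself is captured as a termination reason. All of this stands, and it disposes of several stronger readings that a reader might infer:

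- **That these AEs are lost from the primary safety data.** Not supported. The primary variables are treatment-emergent events, and the core-study data hold the onset.
- **That the rule contradicts Section 9.1.3.** That section says "An AE should be followed until it has resolved, has a stable sequelae", but it does not require every outcome to sit on an N01266 AE page. The outcome may be held with the core study, whose follow-up rules are not shown.
- **That the rule contradicts Section 9.1.2.2.** The pairing rule there ("the AE verbatim term being the same for the first and repeated AE") needs a first record. For a carried-over AE that record exists in the core study under the same subject number.
- **That Table 5-2 footnote j sets a conflicting rule.** It says that "ongoing AEs that stop during EP0065 will be recorded in the N01266 eCRF", but it concerns subjects already in N01266 who visit EP0065 and return. Closing an AE in the study that opened it is consistent with Section 9.1.2.
- **That dose-change or resolution analyses are damaged.** Section 12.3 plans no such tables.
- **That a planned cohort comparison is biased.** None is planned. Section 12.2 says only that results may also be summarized for direct enrollers and by core study.

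The reply does not reach the table of AEs leading to withdrawal. Core-study data can supply the onset of the event, but they were collected before the subject withdrew from N01266. A termination reason is not an AE record.

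**Conclusion.** The point holds in a narrow form. If sites follow Section 9.1.2 exactly, an unworsened core-onset AE that leads to withdrawal from N01266 has no AE record in the study, and the planned table of AEs leading to withdrawal can undercount for LTFU subjects. The direction is known and the group covered is at most about 500 of about 600 subjects. The number of events missed cannot be derived from the Protocol.

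Two assumptions carry this: that the table is built from N01266 AE records, and that no process outside the Protocol updates the core-study AE record when the subject later withdraws. The Protocol describes no such process. The consequence is an incomplete secondary table under the primary safety objective, not a failure of the primary variables. It is a cheap improvement.

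**What to change.** In Section 9.1.2, Table 5-1 footnote f and Sections 8.3.1.1 to 8.3.1.3, add a second exception beside worsening:

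> *An AE ongoing at core-study completion that leads to discontinuation of BRV or withdrawal from N01266, or that becomes serious, is entered in the N01266 eCRF with its original onset date, action taken and outcome, and flagged as having its onset in the core study. It does not count as a new N01266 TEAE unless it worsens. It is included in the table of AEs leading to withdrawal and, if serious, in the SAE table.*

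The clause on seriousness removes doubt: Section 9.1.2 does not say whether becoming serious without a rise in intensity counts as worsening.

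Re-entering every ongoing AE for every LTFU subject is not needed. It would duplicate core-study data without changing any planned table.

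The cost is one flag on the AE page, matching text in the completion guidelines, a few extra entries, and reconciliation of those entries with the core-study records so that pooled safety data do not count them twice. Counts of AEs leading to withdrawal may rise slightly.

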9.1.2.1 Description of adverse events

When recording an AE, the Investigator should use the overall diagnosis or syndrome using standard medical terminology, rather than recording individual symptoms or signs. The eCRF and source documents should be consistent. Any discrepancies between the subject's own words on his/her own records (eg, diary card) and the corresponding medical terminology should be clarified in the source documentation.

Details for completion of the Adverse Event in the eCRF (including judgment of relationship to study medication) are described in the eCRF Completion Guidelines.

Occurrence of COVID-19 in subjects should be reported as either “suspected COVID-19” or “confirmed COVID-19.” For subjects where COVID-19 is still suspected despite a negative viral test, please report as “suspected COVID-19.”

9.1.2.2 Rule for repetition of an adverse event

An increase in the intensity of an AE should lead to the repetition of the AE being reported with:

- the outcome date of the first AE that is not related to the natural course of the disease being the same as the start date of the repeated AE, and the outcome of “worsening”,
- the AE verbatim term being the same for the first and repeated AE, so that the repeated AE can be easily identified as the worsening of the first one.

9.1.2.3 Additional procedures for reporting adverse events

A blood sample for determination of BRV plasma concentration should be obtained for any subject who has an SAE.

If an SAE is reported, UCB must be informed within 24 hours of receipt of this information by the site (see contact numbers for SAE reporting listed in the Serious Adverse Event Reporting section at the front of the protocol). The Investigator must forward to UCB (or its representative) a duly completed Investigator SAE Report form provided by UCB, even if the data are incomplete, or if it is obvious that more data will be needed in order to draw any conclusions. Information recorded on this form will be entered into the global safety database.

An Investigator SAE Report form will be provided to the Investigator. The Investigator SAE Report form must be completed in English.

Additional information (eg, autopsy or laboratory reports) received by the Investigator must be provided within 24 hours. All documents in the local language must be accompanied by a translation in English, or the relevant information included in the same document must be summarized in the Investigator SAE Report form.

The Investigator is specifically requested to collect and report to UCB (or its representative) any SAEs (even if the Investigator is certain that they are in no way associated with the investigational product), up to 30 days from the end of the study for each subject, and to also inform participating subjects of the need to inform the Investigator of any SAE within this period. Any SAEs that the Investigator thinks may be associated with the investigational product must be reported to UCB regardless of the time between the event and the end of the study.

Upon receipt of the SAE form, UCB will perform an assessment of expectedness of the reported SAE. The assessment of the expectedness of the SAE is based on the Investigator's Brochure.

